6.5.2. Dose Delays

Re-treatment following treatment interruption for treatment-related toxicity or at the start of any new cycle may not occur until all of the following parameters have been met:

- ANC $\geq 1,000/\text{mm}^3$.
- Platelets count $\geq 50,000/\text{mm}^3$.

Nonhematologic toxicities have returned to baseline or Grade ≤ 1 severity (or, at the investigator's discretion, Grade ≤ 2 if not considered a safety risk for the participant).

If a treatment delay results from worsening of hematologic or biochemical parameters, the frequency of relevant blood tests should be increased as clinically indicated.

If these conditions are met within 4 weeks of treatment interruption, PF-07260437 may be resumed. Refer to the Dose Reductions Section 6.5.3 for AEs requiring dose reduction at the time of treatment resumption.

If participants require discontinuation of PF-07260437 for more than 4 weeks at any time during the study, then study treatment should be permanently discontinued, unless the investigator's benefit/risk assessment suggests otherwise after discussion with the sponsor. In this situation, if a treatment interruption continues for more than 4 weeks, the day when treatment is restarted will be counted as Day 1 of the next cycle.

6.5.3. Dose Reductions

Following dosing interruption or cycle delay due to toxicity, the PF-07260437 dose may need to be reduced when treatment is resumed.

No specific dose adjustments are recommended for Grade 1 or 2 treatment-related toxicity. However, investigators should always manage their participants according to their medical judgment based on the particular clinical circumstances.

Dose reduction of PF-07260437 by 1 and, if needed, 2 dose levels (See Table 9) will be allowed depending on the type and severity of toxicity encountered. Participants requiring more than 2 dose reductions will be discontinued from the treatment and entered into the Follow-up phase, unless otherwise agreed between the investigator and the sponsor. All dose modifications/adjustments must be clearly documented in the participant's source notes and CRF.

Once a dose has been reduced for a given participant, all subsequent cycles should be administered at that dose level, unless further dose reduction is required. Intraparticipant dose re-escalation is not allowed.

Table 9. Available Dose Reduction Levels From Starting Dose

Dose Level	PF-07260437 SC	PF-07260437 IV
Starting dose	100 µg Q2W	60 µg Q2W
-1	60 ug Q2W (one dose level below starting dose)	N/A

Participants experiencing a DLT may resume dosing at the next lower dose level (if applicable) once adequate recovery is achieved, and in the opinion of the investigator and sponsor, the participant is benefiting from therapy.

In some cases, participants experiencing recurrent and intolerable Grade 2 toxicity may reduce the dose to the next lower dose level once recovery to Grade ≤ 1 or baseline is achieved.

Recommended dose modifications of PF-07260437 for non-immune related toxicity are described in Table 10.

Table 10. Dose Modifications for Study for Non-Immune-Related Toxicity

Toxicity	Grade 1	Grade 2	Grade 3	Grade 4
Nonhematologic (except pancreatitis)	Continue at the same dose level.	Continue at the same dose level.	Withhold dose until toxicity is Grade <1 , or has returned to baseline, then resume treatment at the same dose level or reduce the dose by 1 level at the discretion of the investigator.*	Withhold dose until toxicity is Grade <1 , or has returned to baseline, then reduce the dose by 1 level or 2 levels, or permanently discontinue at the discretion of the investigator.*

Table 10. Dose Modifications for Study for Non-Immune-Related Toxicity

Toxicity	Grade 1	Grade 2	Grade 3	Grade 4
Pancreatitis	Continue at the same dose level.	Withhold dose until toxicity is resolved, then reduce the dose by 1 level.	Consider discontinuation (continuation requires sponsor approval).	Permanent discontinuation of study drug for related Grade 4 adverse events of any duration.
Hematologic	Continue at the same dose level.	Continue at the same dose level.	Withhold dose until toxicity is Grade <2, or has returned to baseline, then reduce the dose by 1 level.	Withhold dose until toxicity is Grade <2, or has returned to baseline, then reduce the dose by 1 level or 2 levels or permanently discontinue at the discretion of the investigator.*

* Nausea, vomiting, or diarrhea must persist at Grade 3 or 4 despite maximal medical therapy to require dose modification.

Recommended dose modifications of study intervention for immune related toxicity are described in Table 11. Please refer to [Section 10.3.5](#) for detailed dose modification and comprehensive management of irAEs.

Table 11. Dose Modifications for Immune-Related Toxicity

Organ System	Grade 1	Grade 2	Grade 3	Grade 4
GI (Diarrhea)	Continue investigational treatment.	Withhold investigational treatment. If improves to Grade 1, resume treatment. If persists >5-7 days or recur treat as Grade 3 or 4.	Withhold investigational treatment. If improves to Grade 1 after treatment, resume investigational therapy at the same dose level or reduce the dose by 1 level at the discretion of the investigator.	Discontinue investigational treatment.
Skin (Dermatitis)	Continue investigational treatment. If persists >1-2 weeks, withhold. If improves after treatment with corticosteroids, then resume investigational treatment.	Continue investigational treatment. If persists >1-2 weeks, withhold. If improves after treatment with corticosteroids, then resume investigational treatment.	Withhold investigational treatment. If improves to Grade 1 after treatment, resume investigational therapy.	Withhold or discontinue investigational treatment. If improves to Grade 1 after treatment, resume investigational therapy.
Lung (pneumonitis)	Consider delay of investigational treatment.	Withhold investigational treatment; re-image.	Discontinue	Discontinue

Table 11. Dose Modifications for Immune-Related Toxicity

Organ System	Grade 1	Grade 2	Grade 3	Grade 4
	Monitor	If symptoms return to baseline, then resume investigational treatment.		
Liver (hepatitis)	Continue investigational treatment.	Withhold investigational treatment; increase monitoring of LFTs; resume investigational therapeutic if labs return to baseline. If elevations persist ≥ 5 to 7 days or worsen, treat with corticosteroids, resume investigational treatment if labs return to Grade 1 or baseline.	Discontinue	Discontinue
Endocrinopathies (hypothyroidism, hyperthyroidism, adrenal insufficiency, type 1 diabetes mellitus)	Continue investigational treatment.	Continue investigational treatment.	Withhold investigational treatment. If improves to Grade 1 after treatment, resume investigational therapy.	Discontinue

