10.3.5. Guidance for Immune-Related Adverse Events

Management of Immune-Related Adverse Events

Gastrointestinal irAEs		
Severity of Diarrhea/Colitis (NCI-CTCAE v5.0)	Initial Management	Follow-up Management
Grade 1 Diarrhea: <4 stools/day over baseline Colitis: asymptomatic	-Continue study treatment -Symptomatic treatment (eg, loperamide)	-Close monitoring for worsening symptoms. -Educate participant to report worsening immediately. -If worsens: Treat as Grade 2, 3 or 4.
Grade 2 Diarrhea: 4 to 6 stools per day over Baseline; IV fluids indicated <24 hours; not interfering with ADL Colitis: abdominal pain; blood in stool	-Withhold study treatment -Symptomatic treatment	-If improves to Grade ≤ 1 : Resume study treatment. -If persists >5-7 days or recurs: Treat as Grade 3 or 4.

Gastrointestinal irAEs		
Severity of Diarrhea/Colitis (NCI-CTCAE v5.0)	Initial Management	Follow-up Management
Grade 3 to 4 Diarrhea (Grade 3): ≥ 7 stools per day over Baseline; incontinence; IV fluids ≥ 24 hours; interfering with ADL Colitis (Grade 3): severe abdominal pain, medical intervention indicated, peritoneal signs Grade 4: life-threatening, perforation	
-Withhold for Grade 3-Permanently discontinue study treatment for Grade 4 or recurrent Grade 3-1.0 to 2.0 mg/kg/day prednisone IV or equivalent-Add prophylactic antibiotics for opportunistic infections-Consider lower endoscopy	
-If improves: Continue steroids until Grade ≤ 1, then taper over at least 1 month; resume study treatment following steroids taper (for initial Grade 3).-If worsens, persists > 3 to 5 days, or recurs after improvement.-Add infliximab 5 mg/kg (if no contraindication).-Note: infliximab should not be used in cases of perforation or sepsis.

Dermatological irAEs		
Grade of Rash (NCI-CTCAE v5.0)	Initial Management	Follow-up Management
Grade 1 to 2 Covering \leq 30% body surface area	
 -Continue study treatment -Symptomatic therapy (for example, antihistamines, topical steroids) 	
 -If persists >1 to 2 weeks or recurs: -Withhold study treatment -Consider skin biopsy -Consider 0.5-1.0 mg/kg/day prednisone or equivalent. Once improving, taper steroids over at least 1 month, consider prophylactic antibiotics for opportunistic infections, and resume study treatment following steroids taper. -If worsens: Treat as Grade 3 to 4.

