Grade 3 to 4 Grade 3: Covering $>$ 30% body surface area; Grade 4: Life threatening consequences	
 -Withhold study treatment for Grade 3 -Permanently discontinue for Grade 4 or recurrent Grade 3 -Consider skin biopsy -Dermatology consult -1.0 to 2.0 mg/kg/day prednisone or equivalent -Add prophylactic antibiotics for opportunistic infections 	
 -If improves to Grade \leq1: Taper steroids over at least 1 month; resume study treatment following steroids taper (for initial Grade 3).

Pulmonary irAEs		
Grade of Pneumonitis (NCI-CTCAE v5.0)	Initial Management	Follow-up Management
Grade 1 Radiographic changes only	
 -Consider withholding study treatment -Monitor for symptoms every 2 to 3 days -Consider Pulmonary and Infectious Disease consults 	
 -Re-assess at least every 3 weeks. -If worsens: Treat as Grade 2 or Grade 3 to 4.
Grade 2 Mild to moderate new symptoms	
 -Withhold study treatment -Pulmonary and Infectious Disease consults -Monitor symptoms daily; consider hospitalization -1.0 to 2.0 mg/kg/day prednisone or equivalent -Add prophylactic antibiotics for opportunistic infections -Consider bronchoscopy, lung biopsy 	
 -Re-assess every 1 to 3 days If improves: -When symptoms return to Grade ≤ 1, taper steroids over at least 1 month, and then resume study treatment following steroids taper. -If not improving after 2 weeks or worsening: Treat as Grade 3 to 4.
Grade 3 to 4 Grade 3: Severe new symptoms; New/worsening hypoxia; Grade 4: Life-threatening	
 -Permanently discontinue study treatment. -Hospitalize -Pulmonary and Infectious Disease consults -1.0 to 2.0 mg/kg/day prednisone or equivalent -Add prophylactic antibiotics for opportunistic infections -Consider bronchoscopy, lung biopsy 	
 -If improves to Grade ≤ 1: Taper steroids over at least 1 month. -If not improving after 48 hours or worsening: Add additional immunosuppression (for example, infliximab, cyclophosphamide, IV immunoglobulin, or mycophenolate mofetil).

Hepatic irAEs		
Grade of Liver Test Elevation (NCI-CTCAE v5.0)	Initial Management	Follow-up Management

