Grade 1 Grade 1 AST or ALT >ULN to 3.0 x ULN and/or Total bilirubin >ULN to 1.5 x ULN	-Continue study treatment	-Continue liver function monitoring -If worsens: Treat as Grade 2 or 3 – 4.
Grade 2 AST or ALT >3.0 to \leq 5 x ULN and/or total bilirubin >1.5 to \leq 3 x ULN	-Withhold study treatment -Increase frequency of monitoring to every 3 days	-If returns to Grade \leq 1: Resume routine monitoring; resume study treatment. -If elevation persists >5 to 7 days or worsens: Treat as Grade 3 to 4.
Grade 3 to 4 AST or ALT >5 x ULN and/or total bilirubin >3 x ULN	-Permanently discontinue study treatment -Increase frequency of monitoring to every 1 to 2 days -1.0 to 2.0 mg/kg/day prednisone or equivalent -Add prophylactic antibiotics for opportunistic infections -Consult gastroenterologist/hepatologist -Consider obtaining MRI/CT scan of liver and liver biopsy if clinically warranted	-If returns to Grade \leq 1: Taper steroids over at least 1 month. -If does not improve in >3 to 5 days, worsens or rebounds: Add mycophenolate mofetil 1 gram (g) twice daily. -If no response within an additional 3 to 5 days, consider other immunosuppressants per local guidelines.

Renal irAEs		
Grade of Creatinine Increased (NCI-CTCAE v5.0)	Initial Management	Follow-up Management
Grade 1 Creatinine increased >ULN to 1.5 x ULN	-Continue study treatment	-Continue renal function monitoring. -If worsens: Treat as Grade 2 to 3 or 4.
Grade 2 to 3 Creatinine increased >1.5 and \leq 6 x ULN	-Withhold study treatment -Increase frequency of monitoring to every 3 days -1.0 to 2.0 mg/kg/day prednisone or equivalent. -Add prophylactic antibiotics for opportunistic infections -Consider renal biopsy	-If returns to Grade \leq 1: Taper steroids over at least 1 month, and resume study treatment following steroids taper. -If worsens: Treat as Grade 4.
Grade 4 Creatinine increased >6 x ULN	-Permanently discontinue study treatment -Monitor creatinine daily -1.0 to 2.0 mg/kg/day prednisone or equivalent. -Add prophylactic antibiotics for opportunistic infections -Consider renal biopsy -Nephrology consult	-If returns to Grade \leq 1: Taper steroids over at least 1 month.

Cardiac irAEs		
Myocarditis	Initial Management	Follow-up Management

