Grade 3 or Grade 4 endocrinopathies (hypothyroidism, hyperthyroidism, adrenal insufficiency, type I diabetes mellitus)	
 -Withhold study treatment -Consider hospitalization -Endocrinology consult -Start thyroid hormone replacement therapy (for hypothyroidism), anti-thyroid treatment (for hyperthyroidism), corticosteroids (for adrenal insufficiency) or insulin (for type I diabetes mellitus) as appropriate -Rule-out secondary endocrinopathies (ie, hypopituitarism / hypophysitis) 	
 -Resume study treatment once symptoms and/or laboratory tests improve to Grade ≤ 1 (with or without hormone replacement/suppression). -Continue hormone replacement/suppression and monitoring of endocrine function as appropriate.
Hypopituitarism/ Hypophysitis (secondary endocrinopathies)	
 -If secondary thyroid and/or adrenal insufficiency is confirmed (ie, subnormal serum free T4 with inappropriately low TSH and/or low serum cortisol with inappropriately low ACTH): -Refer to endocrinologist for dynamic testing as indicated and measurement of other hormones (FSH, LH, GH/IGF-1, PRL, testosterone in men, estrogens in women) -Hormone replacement/suppressive therapy as appropriate -Perform pituitary MRI and visual field examination as indicated -If hypophysitis is confirmed: -Continue study treatment if mild symptoms with normal MRI. Repeat the MRI in 1 month -Withhold study treatment if moderate, severe, or life-threatening symptoms of hypophysitis and/or abnormal MRI. Consider hospitalization. Initiate corticosteroids (1 to 2 mg/kg/day prednisone or equivalent) followed 	
 -Resume study treatment once symptoms and hormone tests improve to Grade ≤ 1 (with or without hormone replacement). -In addition, for hypophysitis with abnormal MRI, resume study treatment only once shrinkage of the pituitary gland on MRI/CT scan is documented. -Continue hormone replacement/suppression therapy as appropriate.

Endocrine irAEs		
Endocrine Disorder	Initial Management	Follow-up Management
	
by corticosteroids taper during at least 1 month
 
-Add prophylactic antibiotics for opportunistic infections
	

Other irAEs (not described above)		
Grade of other irAEs (NCI-CTCAE v5.0)	Initial Management	Follow-up Management

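### Protocol Table 11 and Section 10.3.5 give inconsistent stop-or-resume rules for endocrine Grade 4, skin Grade 4 and unresolved liver Grade 2 events, and no text says which prevails

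*Protocol*

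**What the plan says.** Table 11 in Protocol Section 6.5.3 gives one action per organ system and grade.

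- **Skin, Grade 4:** "Withhold or discontinue investigational treatment. If improves to Grade 1 after treatment, resume investigational therapy".
- **Liver, Grade 2:** treatment is withheld. If the elevation lasts about 5 to 7 days or worsens, the instruction is to "treat with corticosteroids, resume investigational treatment if labs return to Grade 1 or baseline".
- **Endocrine:** the row is labelled "Endocrinopathies (hypothyroidism, hyperthyroidism, adrenal insufficiency, type 1 diabetes mellitus". Its Grade 3 cell is withhold and resume at Grade 1; its Grade 4 cell is discontinue.

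Section 10.3.5 covers the same organ systems.

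- **Skin:** "Permanently discontinue for Grade 4 or recurrent Grade 3". Resumption after the steroid taper is reserved for a first Grade 3 event.
- **Liver, Grade 2:** "If elevation persists >5 to 7 days or worsens: Treat as Grade 3 to 4". The Grade 3 to 4 row orders permanent discontinuation and offers no route back.
- **Endocrine:** a single row covers "Grade 3 or Grade 4 endocrinopathies (hypothyroidism, hyperthyroidism, adrenal insufficiency, type I diabetes mellitus". The action is to withhold, and the follow-up is "Resume study treatment once symptoms and/or laboratory tests improve to Grade" 1 or lower, with or without hormone replacement.

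Four places link the two texts. Section 6.5 tells sites to manage potentially drug-related toxicities by Tables 10 and 11. The next paragraph of Section 6.5 sends selected toxicities that fail to resolve or that worsen, look immune-related and may need corticosteroids to Section 10.3.5. Section 6.5.3 calls the Table 11 modifications recommended and refers to Section 10.3.5 for the detail. Section 6.8.2.6 describes Section 10.3.5 as guidelines.

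**The concern.** A site can follow a written instruction in one section and re-dose a participant whom another section bars from further treatment. That can happen after life-threatening skin toxicity, or after a Grade 2 hepatitis that persisted and then settled on corticosteroids. For a Grade 4 endocrinopathy controlled on hormone replacement, one text ends treatment and the other lets it continue.

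This is a multi-centre first-in-human study of a T-cell engager. The Protocol expects irAEs (Section 2.3) and uses no data monitoring committee (Section 10.1.5.1). The first stake is participant safety. The second is consistency: the same event could lead to discontinuation at one site and resumption at another, and the planned summaries of adverse events leading to withdrawal from treatment (Protocol Section 9.3.5.2) would then partly reflect which text a site followed.

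**Working it through.** No figure in the plan needs reproducing. The check compares the two texts cell by cell on one criterion: must treatment end permanently, or may it resume?

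**The three cells that differ**

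| Event | Table 11 | Section 10.3.5 | Stricter text | Can one action satisfy both? |
|---|---|---|---|---|
| Endocrine Grade 4 | Discontinue | Withhold; resume at Grade 1 or lower | Table 11 | No, once the event has improved |
| Skin Grade 4 | Withhold or discontinue; resume at Grade 1 | Permanently discontinue | 10.3.5 | Yes, if the site discontinues |
| Liver Grade 2, persisting or worsening within Grade 2 | Corticosteroids; resume at Grade 1 or baseline | Treat as Grade 3 to 4: permanently discontinue | 10.3.5 | No, once the labs have recovered |

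Two limits apply. If liver Grade 2 worsens to Grade 3, Table 11's own Grade 3 cell says discontinue, so the texts agree; the liver conflict covers only persistence and worsening within Grade 2. For skin Grade 4 the conflict is partial: Table 11 permits what Section 10.3.5 forbids, but does not require it.

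**Count.** Table 11 has 5 organ systems × 4 grades = 20 cells. On the criterion above, 3 are inconsistent. Another 3 are silent on a stopping condition that Section 10.3.5 adds: GI Grade 3 ("Permanently discontinue study treatment for Grade 4 or recurrent Grade 3"), skin Grade 3 (recurrence) and lung Grade 2 (no improvement after 2 weeks, or worsening). The remaining 20 − 3 − 3 = 14 agree. Differences in the recovery threshold (baseline versus Grade 1 or lower) and in steroid-taper timing were not counted.

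**Is precedence stated?**

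1. Section 6.5 points to Tables 10 and 11 and then, for selected unresolved or worsening irAE-like toxicities, to Section 10.3.5. The second pointer fits persistent liver Grade 2 needing corticosteroids reasonably well. It does not say which toxicities are selected, nor that Table 11 yields.
2. Section 6.5.3 sends the reader to Section 10.3.5 for more detail. That suggests the appendix is the fuller text, but gives no rule for a contradiction.
3. The Grade 4 row for other irAEs in Section 10.3.5 requires permanent discontinuation, but covers only irAEs not described in the earlier tables. It does not settle the endocrine or skin case.

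Reading every pointer as favouring Section 10.3.5 would still leave the endocrine question open in substance, because there Section 10.3.5 is the more permissive text.

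**The case against.** The best defence is that the Protocol already ranks the texts in practice: Table 11 is a recommended summary, Section 6.5.3 sends the reader to Section 10.3.5 for detail, and Section 6.5 routes unresolved irAE-like toxicities there. This has force, most of all for liver Grade 2. It falls short of a rule, since Section 6.5 also tells sites to act on Table 11.

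A second defence is sponsor oversight. Section 8 requires immediate discussion with the sponsor on whether a participant continues, and Section 6.5.2 makes permanent discontinuation the default after more than 4 weeks off drug. With the steroid tapers of at least 1 month in Section 10.3.5, that default could often apply to steroid-treated skin and liver events. These safeguards reduce the risk. They do not remove it: the discussion has no agreed rule to apply, the 4-week default can be set aside on a benefit/risk assessment after sponsor discussion, and an event that settles sooner never reaches it.

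A reader might infer two stronger points that the documents do not support.

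- **That the three silent cells are also contradictions.** Table 11 refers to Section 10.3.5 for detail, and a summary that leaves out a recurrence or non-improvement rule does not contradict the text it cites. For lung Grade 2, Table 11 also allows resumption only once symptoms are back to baseline.
- **That the sentence in Section 6.5.3 on resuming after a DLT is a third rule, overriding discontinuation even for Grade 3 or 4 pneumonitis.** That sentence is general and permissive, and it requires the investigator and sponsor to judge that the participant is benefiting. Reading it as displacing two specific instructions to discontinue is strained.

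**Conclusion.** The concern holds for three cells of Table 11. Endocrine Grade 4 and liver Grade 2 (persisting, or worsening within the grade) are direct conflicts; skin Grade 4 is a partial one. Neither text is uniformly the safer: Table 11 is stricter for endocrine Grade 4, and Section 10.3.5 for the other two. The liver conflict is the best covered by existing cross-references. No text states precedence for any of the three.

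This is a drafting inconsistency with a safety consequence, and it should be corrected. A reader might take it to affect dose-finding directly; the DLT definition in Section 4.3.6 refers to neither text, and a Grade 4 irAE in the DLT window counts as a DLT under that definition whichever dosing rule is followed. The size is 3 of 20 cells. Without expected irAE rates in the documents, the number of participants affected cannot be estimated. The conclusion assumes that sites apply the tables as written.

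**What to change.** 1. Have the sponsor choose one endocrine Grade 4 rule and use it in both places. If resumption is chosen, change the Table 11 cell. If discontinuation is chosen, split the combined Grade 3 or 4 row in Section 10.3.5. Do this first, because a precedence sentence alone would select resumption by default.
2. Change the Table 11 skin Grade 4 cell to permanently discontinue.
3. Change the Table 11 liver Grade 2 cell so that persistent or worsening elevation is treated as Grade 3 to 4.
4. State in Section 6.5.3 that Section 10.3.5 governs irAE dose modification where the texts differ.

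Optional harmonisation, not correction of errors: add to Table 11 permanent discontinuation for recurrent Grade 3 GI or skin events, and treatment as Grade 3 to 4 for lung Grade 2 that is not improving after 2 weeks or is worsening. Also qualify the DLT resumption sentence with an exception where Table 11 or Section 10.3.5 requires permanent discontinuation.

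The cost is protocol wording: two Table 11 cells, one precedence sentence, and either a third cell or a split row in Section 10.3.5. The optional edits add three cells and one clause. Sample size, assessments and analyses do not change.
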